#### C. Devices

Participants who do not have a mobile phone of their own will be given a low-cost mobile device (~\$30/unit) with a 12-month talk and text plan (~\$125/year through Tracfone) to facilitate communication and follow-up. If a participant loses or sells their device, the phone will not be replaced, and their plan will be deactivated. To incentivize phone retention, participants who still have their device at the end of the study will be allowed to keep it.

#### D. Procedures

There will be no procedures or surgical interventions in this study.

#### E. Data Collection

All data will be collected using password-protected, Mass General Brigham-approved laptops or tablets with full-disk encryption. We will use the Mass General Brigham-hosted Research Electronic Data Capture (REDCap) application for data collection and management. The specific data elements collected at each study visit are detailed below in section VI.

#### F. Electronic Communication

The Twilio text messaging feature will be integrated into our REDCap database. This will allow study staff to send participants automated text message reminders about their next scheduled appointment and the maximum potential payment they can earn at this visit. Text messages will not include any identifying information and participants can opt out at any time by texting the word “STOP” (see Appendix 1 for sample text messages). Participants must consent to receive these text messages. The consent form includes information outlined in the Mass General Brigham guidelines for texting research subjects.

Study staff may use Mass General Brigham’s HIPAA-compliant video conference platforms, Microsoft Teams or Enterprise Zoom, to administer surveys and complete coaching sessions as part of the team’s in-person remote COVID-19 safety protocol (see section V.A). Participants who prefer this form of engagement will arrive to the BHCHP clinic where on-site study staff will set up a Teams or Zoom call on a study tablet for the participant to use. Participants will participate in the video call using headphones in a private or semi-private space within the clinic; study staff will administer the survey or complete the coaching session via Teams or Zoom either on-site (in a separate room) or remotely. This will minimize in-person contact between study staff and participants while allowing participants and study staff to engage in potentially sensitive conversations during the surveys and coaching sessions. For safety and security, no Teams or Zoom links will be shared with participants. Teams or Zoom meetings will require passwords and will not be shared with anyone other than study staff. Participants will be instructed not to use the chat function during these meetings as the feature is not encrypted. Participants will also be advised that photographs and recordings of Teams or Zoom calls are not allowed.

Participants may meet with the study clinician via MGB-hosted Microsoft Teams, MGB Enterprise Zoom, or BHCHP's Epic/OCHIN integrated HIPAA-compliant Zoom platform. The third option allows participants to engage with the clinician in the manner currently used to provide COVID-safe virtual clinical care at BHCHP.

Study staff may also engage with participants over the phone. If participants prefer remote virtual study visits for COVID-19 precautions, study staff will conduct surveys, coaching visits, interviews, and some clinician visits over the phone. Study staff will call participants from study cellphones or BHCHP land lines. Participants will provide a contact number during the enrollment visit and can update the contact number as necessary.

Study staff may use Imprivata cortex, a HIPAA-compliant secure communications platform, to communicate with the study clinician using designated work iPhones encrypted with iOS MobileIron Mobile Device Management (MDM) software.

#### G. COVID-19 Contingency Plans:

The team is engaged in contingency planning and will continue to monitor hospital, state, and federal guidance on COVID-19. Should a resurgence of COVID interfere with the ability to implement the study protocol as written here, the team will implement contingency plans that will be adopted for the circumstances and restrictions present at the time of a future surge.

Participants and staff will be asked to follow current CDC guidelines regarding isolation and/or quarantine in the event of developing COVID-19 symptoms or experiencing a significant COVID-19 exposure. The implications of COVID-related absences for incentive arm payments are discussed above.

#### H. Procedures for Restarting Enrolled Participants

As described in protocol amendment 11, all study activities were paused on 07/06/21 due to a global shortage of varenicline resulting from elevated levels of nitrosamine contaminants prompting a recall of all Pfizer-manufactured varenicline on the market. The safety considerations related to this are addressed in section VII.B. At the time of study suspension, 11 participants were enrolled.

Once the study resumes, the 11 participants who were previously enrolled will be approached by phone or in person to be invited to restart the study. Participants interested in restarting the study will do so under their original study ID number and randomized group assignment but will be asked to redo all other study activities. If participants are interested in restarting the study, they will be asked to complete the eligibility screener questions and saliva test (see section V.A.1.) to confirm their continued eligibility before completing two study restart appointments as described below.

To ease the response burden, participants will be offered the option to complete the eligibility screener questions over the phone. If their responses to the questions suggest that they are still eligible to participate, they will be invited to meet with study staff in person at JYP within two weeks to confirm their eligibility with a saliva test for cotinine. If the cotinine saliva test is consistent with current smoking, participants will immediately proceed with the first study restart appointment. Participants who opt to complete all components of the eligibility re-screening in person will meet with study staff at JYP and, if still eligible, will be invited to complete the first study restart appointment either immediately or within 2 weeks. Participants who are found to no

longer be eligible during any component of the eligibility re-screening process will be given the option to either screen again at a later date (if the reason for ineligibility is a time-limited issue such as connectedness to care) or to unenroll from the study.

At the first study restart appointment, participants will follow procedures similar to the enrollment appointment discussed in section V.A.2. Study staff will review an updated version of the consent form with participants, and participants will be required to sign this updated version of the consent form to continue study participation. Study staff will then confirm participants' current demographic and contact information and repeat the full baseline survey. Participants will receive \$25 for completing this first appointment. Following this first appointment, all PCPs will be messaged using the same procedures described in sections V.A.4 and V.B. PCPs will need to give permission for the study clinician to prescribe varenicline for participants who report various health concerns during their most recently-completed eligibility screener and baseline survey.

The second study restart appointment must be completed within 4 weeks of the first study restart appointment. Participants will follow the same procedures described in sections V.A.3 and V.A.4, with the exception that participants who were previously randomized will retain their original treatment group assignment. Participants who do not have their own phone will be offered a study phone and will be paid \$10 for completing this study visit.

Participants who complete both the first and second appointments will restart the study at week 0, which corresponds with the quit date and first tobacco coaching session, approximately 1 week after their second study restart appointment.

All data collected during the original study launch prior to the pause will be exported from REDCap and archived in the secure Lab Archives system to allow for a clear audit trail of any changes to the data. In REDCap, new instances of forms will be created for any repeatable forms, and new data will overwrite old data as needed for non-repeatable forms. Study staff will log all instances of updates to existing non-repeatable forms within REDCap. The most recent data will be used for analyses and earlier data will be disregarded.

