## III. SUBJECT SELECTION

## A. Inclusion and exclusion criteria

To be eligible to participate, individuals must meet **all** of the following criteria:

- 1) Aged  $\geq 18$  years old, assessed by self-report and verified by date of birth.  
*Rationale:* We wish to focus only on adult smokers since adolescent smokers present unique issues that merit separate consideration.
- 2) Lifetime smoker of  $\geq 100$  cigarettes with current daily smoking of  $\geq 5$  cigarettes/day, verified by a saliva cotinine level  $\geq 30$  ng/mL.  
*Rationale:* In order to document smoking abstinence via saliva cotinine levels, trial participants must smoke a sufficient number of cigarettes per day at baseline to be above the accepted threshold of 30 ng/ml for determining smoke exposure.
- 3) Ready to try to quit smoking within the next 3 months, assessed by self-report.  
*Rationale:* We wish to focus on smokers interested in quitting in the near future in order to better isolate a treatment effect.
- 4) Proficient in English, assessed with items asking about native language and self-reported comfort communicating in English among non-native speakers.  
*Rationale:* We do not have the resources to develop study materials or conduct in-person counseling in languages other than English.
- 5) Currently or formerly homeless, assessed by self-report and defined as having ever stayed in an emergency shelter, transitional shelter, abandoned building, place of business, car or other vehicle, church or mission, hotel or motel, or anywhere outside, or having ever stayed in somebody else's house, apartment/condominium, or room due to not having their own place to stay.  
*Rationale:* BHCHP and most HCH programs nationally continue to serve patients after they have gained housing. Additionally, currently and formerly homeless people smoke at similarly high rates, and our epidemiologic analysis of tobacco-attributable cancer and mortality disparities experienced by BHCHP patients included both currently and formerly homeless individuals.
- 6) Have a primary care provider (PCP) within the BHCHP system.  
*Rationale:* This will help ensure that we can communicate efficiently with participants' PCPs via secure, EHR-based messaging systems regarding the safe use of varenicline for smoking cessation.

Individuals will be excluded if they meet **any** of the following criteria:

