**2) Enrollment visit:** The enrollment visit will occur within 2 weeks after completing the screening visit. If more than 2 weeks has elapsed since screening, participants will need to be rescreened before proceeding to enrollment. During the enrollment visit, eligible participants will provide written informed consent. Enrolled participants will then complete a baseline assessment that includes measurement of the specific data variables listed in section VI.A and a demographics/contact form that includes data variables listed in section VI.A. Participants will also be provided with their CT Payer cards (listed below in section XI.A) during this visit upon completion of the baseline assessment survey. Participants will receive \$25 for completing the

baseline survey. Prior to randomization visits, CRCs will look up enrolled participants in the BHCHP electronic health record (EHR) and will complete a chart review form (data variables to collect listed in section VI.A). Enrolled participants will then be randomized to a study arm in the manner described above.

**3) Randomization and baseline clinician visit:** The randomization and baseline clinician visit will occur within 4 weeks after completing the enrollment visit. If more than 4 weeks has passed since enrollment, participants will first need to undergo repeat screening to confirm their continued eligibility, followed by reassessment of baseline survey measures to inform randomization and identify conditions relevant to varenicline use (see below), before being allowed to proceed to randomization. During the randomization visit, study staff will reveal the participant's group assignment and set up the introductory video which will explain the study components and the study schedule. After the introductory video, staff will provide participants with a study cell phone if applicable (see section V.C.). The participant will then be seen by the study clinician, as described in more detail below. During this visit, participants will be encouraged to set a quit date for the following week. Participants will receive \$10 for attending this visit.

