### C. Statistical Methods

**Quantitative analysis:** Quantitative analysis will be based on the intention-to-treat principle. We will use Chi-squared tests to assess the difference between arms on attainment of the primary and secondary outcomes. Cochran-Mantel-Haenszel tests will determine whether the intervention effect is homogenous across study sites. We will use logistic regression to assess the intervention effect while adjusting for site. In primary analysis, participants who do not provide a saliva sample or are lost to follow-up will be assumed non-abstinent. A sensitivity analysis will use multiple imputation to impute missing outcomes data based on non-missing variables. In addition to cross-sectional analyses of the primary and secondary outcomes, we will conduct a repeated measures analysis of smoking status at 12 and 24 weeks to assess the overall impact of financial incentives on smoking abstinence. This analysis, which provides greater statistical power than cross-sectional analyses, will use generalized estimating equations (GEE) to account for the correlated data structure. We will also use GEE to analyze the other outcomes of changes in cigarette consumption, WHO ASSIST drug and alcohol scores, and mental health scores, each measured at baseline and 12 and 24 weeks.

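### Does barring pre-pause participants who have stopped smoking from restarting leave a hole in the intention-to-treat analysis at week 12?

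*Combined protocol and SAP*

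**What the plan says.** Section V.H of the protocol deals with the 11 participants who were enrolled when the study was suspended. Those who wish to restart keep their study number and repeat the screener and the saliva test. On a positive test, "If the cotinine saliva test is consistent with current smoking, participants will immediately proceed with the first study restart appointment". Those who prove ineligible may screen again "if the reason for ineligibility is a time-limited issue such as connectedness to care) or to unenroll from the study". At the second restart appointment, "participants who were previously randomized will retain their original treatment group assignment". A new week 0 is given only to those who complete both appointments. On data handling, V.H says: "The most recent data will be used for analyses and earlier data will be disregarded".

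Section V.A.3 shows that participants know their arm, since at the randomisation visit "study staff will reveal the participant's group assignment". Section III.A gives the reason for a cotinine requirement at baseline: "In order to document smoking abstinence via saliva cotinine levels, trial participants must smoke a sufficient number of cigarettes per day at baseline".

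The analysis rules are in section VI.C: "Quantitative analysis will be based on the intention-to-treat principle". In the primary analysis, "participants who do not provide a saliva sample or are lost to follow-up will be assumed non-abstinent". A sensitivity analysis imputes missing outcomes. The week-12 endpoint in VI.B needs both self-reported 7-day abstinence and a saliva cotinine below 10 ng/mL.

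**The concern.** For a participant already randomised, the restart test comes after randomisation and depends on smoking status, which is what the trial measures. The arm has been disclosed, so quitting before re-screening could differ by arm. V.H does not say that unenrolling leaves a randomised person in the analysis set, and its rule on earlier data does not mention people with no later data.

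Two readings seem open. If such people are dropped, the primary comparison loses randomised participants because of their smoking status. If they are kept, they have no week-12 sample and are scored as smokers despite a negative test at re-screening. With the choice unwritten in an open-label trial, it might be made after results are visible. What would be at stake is the integrity of the 12-week comparison between arms.

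**Working it through.** **Who could be affected.** Enrolment and randomisation are separate visits, up to 4 weeks apart (V.A), and V.H speaks of those who were previously randomised. So between 0 and 11 people are concerned: 11/180 = 6.1% at most. Only those who had quit by re-screening matter, and the documents give no count of them.

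**What the text does with them.** VI.C bases the quantitative analysis on intention to treat and scores anyone without a sample as non-abstinent. No analysis rule removes a participant for unenrolling; that word appears in a procedures section about taking part. Read together, the sections keep the person in the assigned arm as non-abstinent and treat the outcome as missing in the imputation analysis. A negative point-of-care result (below 30 ng/ml) at re-screening is not the week-12 endpoint (below 10 ng/mL plus self-report), so no observed primary outcome is overwritten.

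**The plan's power figure.** Inputs from VI.D: 90 per arm, p1 = 0.04, p2 = 0.175, two-sided 0.05. With pooled variance under the null:

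- mean rate = (0.04 + 0.175)/2 = 0.1075
- SE0 = √(0.1075 × 0.8925 × 2/90) = 0.0462
- SE1 = √[(0.04 × 0.96 + 0.175 × 0.825)/90] = 0.0451
- power = Φ[(0.135 − 1.96 × 0.0462)/0.0451] = 83.8%

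Exact enumeration of the uncorrected chi-squared test gives 86.9%. The stated figure of more than 80% is reproduced.

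**Size of the effect, by illustration.** Assume that all 11 were randomised and split 5/6 or 6/5, that the planned week-12 rates already apply at re-screening, and that nobody who restarts then becomes abstinent. These are assumed values, not a bound.

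- Expected barred quitters: incentives 0.175 × 5 = 0.875 to 0.175 × 6 = 1.05; control 0.04 × 5 = 0.20 to 0.04 × 6 = 0.24.
- Chance of no incentive-arm quitter: 0.825⁵ = 38% or 0.825⁶ = 32%.
- Scored non-abstinent, 5 control and 6 incentives: 0.175 × 84/90 − 0.04 × 85/90 = 16.33% − 3.78% = 12.56 points. With 6 and 5: 16.53% − 3.73% = 12.79 points. The planned difference is 13.5.
- Quitters removed instead: 14.7/88.95 − 3.4/89.8 = 12.74 points, or 14.875/89.125 − 3.36/89.76 = 12.95 points.

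The two readings differ by less than 0.2 points.

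| Handling of all 11 | Normal approximation | Exact |
|---|---|---|
| Kept, non-abstinent (5/6 or 6/5) | 80.5% or 81.7% | 83.9% or 85.1% |
| Excluded (5/6 or 6/5) | 81.5% or 81.4% | 84.3% or 85.1% |

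The extreme in which all 11 sit in the incentives arm and count as non-abstinent gives 73.5% by the normal approximation. Under unrestricted 1:1 allocation that split has probability 0.5¹¹, about 0.05%.

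**Sensitivity of a result.** One participant is 1/90 = 1.1 points of an arm's rate. Near the planned counts, 4/90 against 16/90 gives p = 0.0044. One incentive-arm event fewer (15/90) gives p = 0.0076, and four fewer (12/90) still gives p = 0.036. At the planned rates, the chance that losing exactly one incentive-arm event turns a significant result into a non-significant one is 5.2%.

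**The case for a change.** The best case for a change is that the rule should be written because it is cheap. Arms are known, outcomes are monitored on a rolling basis (IX.E) and analyses run periodically (IX.A), so an unwritten choice could be settled after data are seen. Nor is the direction always conservative, since excluding control-arm quitters would favour incentives. If three control participants had quit (an assumed number), excluding them gives 4/87 against 16/90, p = 0.0056, whereas counting them as abstinent gives 7/90 against 16/90, p = 0.044.

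Part of this stands. V.H does not state that unenrolment leaves a randomised person in the analysis set, and it gives no week-12 date for someone who never restarts. But the larger contrast in that example comes from counting the quitters as abstinent, which the plan does not provide for. Under VI.C they are non-abstinent, so 4/90 against 16/90 gives p = 0.0044, close to the 0.0056 from excluding them.

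The obvious remedies add little. Stating that everyone randomised stays in the analysis repeats VI.C. Treating the outcome as missing either leaves the primary analysis as it is, because missing already means non-abstinent, or makes an exception to that rule. An extra analysis of those randomised after resumption, and restart counts by arm, would be informative but would correct no wrong result.

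Two further points weaken the concern. The time-limited reasons in V.H are introduced by an example, not a closed list, so a negative test need not bar someone for good, although a quitter could return only after smoking again. And for a person with no later record, the pre-pause record is the most recent one.

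**Conclusion.** No change follows. The restart section is silent on one detail, and the general analysis rules fill it: a randomised participant who does not restart stays in the assigned arm, counts as non-abstinent in the primary analysis and is imputed in the sensitivity analysis. The cotinine requirement has a stated purpose for a fresh baseline.

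At most 11 of 180 participants are involved, possibly none. In the illustration about one incentive-arm participant is affected, the expected difference shrinks by less than one point (13.5 to about 12.6-12.8), and the shift is against the incentive hypothesis. The power statement holds for any near-even split; only the improbable case of all 11 in the incentives arm and non-abstinent takes it below 80%.

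This rests on reading intention to treat in its ordinary sense, so that unenrolling ends participation without undoing randomisation. It also rests on the assumed split and rates, because the documents do not say how many were randomised before the pause or how many had quit.

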#### B. Drug side effects and toxicities

Participants will be offered a prescription for varenicline. Common side effects of varenicline are nausea, sleep problems, constipation, gas, and vomiting. Other possible, but less common, side effects include cardiovascular (chest pain, hypertension, tachycardia), sleep walking, allergic reactions, or serious skin reactions. Participants who are taking varenicline prescribed by the study clinician will be assessed for varenicline side effects and suicidality at each on-treatment monitoring visit. Procedures for addressing participants with significant side effects and suicidality are described below (section IX. D.).

In June 2021, Pfizer announced a halt in global distribution of varenicline (brand name: Chantix) and a voluntary recall of selected lots after finding heightened levels of N-nitroso-varenicline (a nitrosamine compound) in some pills. Although the risk posed by N-nitroso-varenicline is uncertain, nitrosamine compounds in general are considered carcinogenic when exposure occurs in sufficient doses over prolonged periods of time. The nitrosamine levels found in Pfizer's varenicline product exceeded the FDA's acceptable intake limit of 37 ng per day. In September 2021, Pfizer extended its recall to all lots of varenicline.

The FDA has since approved two generic versions of varenicline: one manufactured by Apotex and one manufactured by Par Pharmaceuticals. The FDA also announced that they would not object to manufacturers distributing varenicline tablets above the FDA's original acceptable intake limit of 37 ng per day but below an interim acceptable intake limit of 185 ng per day. Both of the above generic versions of varenicline distributed by Apotex and Par have levels of N-nitroso-varenicline that are within the FDA's interim acceptable intake limit.

Study staff are working closely with the BHCHP pharmacy to ensure participants receive a varenicline product that falls within these interim safe limits. During informed consent, staff will inform participants of the risk of contamination of varenicline products while also clarifying that the versions they will receive have been deemed safe by the FDA.

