unexpected if the nature, severity, or frequency of the event is not consistent with a known or foreseeable risk given the research procedures, the characteristics of the subject population, or with an expected progression of an underlying condition. The following attribution scale will be used to describe the relationship of the adverse event to the study protocol: unrelated, possibly related, or related to the protocol.

Unexpected adverse events that are at least possibly related to the research and suggest the research puts participants at increased harm will be reported to the Mass General Brigham IRB and Data and Safety Monitoring Board (DSMB; see section H below) within 5 working days or 7 calendar days. Serious adverse events that are unexpected and at least possibly related to the research will be assumed to suggest that the research puts participants at increased risk of harm and will be reported to the Mass General Brigham IRB and DSMB within the same time frame. Any action resulting in a temporary or permanent suspension of this study will be reported to the NIH funding agency's program official. A summary safety report detailing all adverse events and their handling will be included in annual study progress reports to the Mass General Brigham IRB (if requested) and the NIH funding agency. Adverse event reports and annual safety summaries will be documented by study ID number; personal identifiers will not be included in these reports.

**3) Reporting mechanisms to NCI and DSMB:** The PI will report reportable events to the NCI Project Officer by phone or email within 5 working days and follow-up with a written report (by fax or email) within 10 calendar days, detailing any additional information and whether or not the event is related to participation in the study or may affect future participation in the study.

The PI will make a report to the Chairperson of the DSMB within 5 working days of learning of the event. The DSMB will review the event (usually on the phone or via email) and make a report via email to the PI, who will forward the report to the IRB and NCI Project Officer.

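### The restart rule in Section V.H sets aside pre-pause data in analyses without exempting safety and varenicline-exposure data

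*Combined protocol and SAP*

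**What the plan says.** Section V.H covers people who were in the study when it stopped for the varenicline shortage: "At the time of study suspension, 11 participants were enrolled". Those who restart keep their study ID and arm and redo everything else. On data, the section says three things:

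- Retention: "All data collected during the original study launch prior to the pause will be exported from REDCap and archived in the secure Lab Archives system".
- Form handling in REDCap: "new instances of forms will be created for any repeatable forms, and new data will overwrite old data as needed for non-repeatable forms", with updates to non-repeatable forms logged.
- Analysis: "The most recent data will be used for analyses and earlier data will be disregarded".

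Section VI.A (item 3) lists varenicline use, pill counts, side effects and a modified C-SSRS among the data collected at monitoring visits, where applicable. Section VI.B (item 3) names varenicline use among the other outcomes. Section VI.C defines no adverse-event analysis, exposure analysis or safety population.

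Adverse events also have their own route. Section IX.F requires an individual report for each event and promises that "A summary safety report detailing all adverse events and their handling will be included in annual study progress reports". Section IX.H has the DSMB review adverse events.

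**The concern.** For efficacy the rule is sensible: a person who starts again from week 0 should be judged on the restarted course. For safety and exposure the same logic does not apply. A side effect during a partial first course happened to a randomised participant on study-prescribed drug, and a second course does not cancel it. Someone treated twice would also be counted as treated once.

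The data at issue have some particular interest, because the pause arose from contamination of the marketed product. Section VII.B records that "In September 2021, Pfizer extended its recall to all lots of varenicline". If any of the 11 took varenicline before the pause, that exposure preceded the restart arrangements in which the pharmacy is to supply product within the interim nitrosamine limit. What is at stake is a complete account of harms and exposure in the reported results.

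**Working it through.** The plan attaches no figure to the restart rule, so there is none to reproduce. The power statement in Section VI.D concerns 12-week abstinence and is not touched.

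**Step 1: what the rule covers.** The archiving sentence refers to all data from the first launch. The analysis sentence closes the same paragraph and contains no restriction by data type. Side effects, C-SSRS results and varenicline use are monitoring-visit data under VI.A, so they fall inside it. For varenicline use there is no doubt that an analysis is meant, because VI.B lists it as an outcome.

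**Step 2: what remains outside the rule.** The individual reports and annual summaries in IX.F and the DSMB review in IX.H exclude no pre-pause events. Section IX.A adds that the biostatistician analyses prepared data files periodically and that findings go into annual progress reports. The plan does not say whether side-effect ratings and C-SSRS results reach the reported results through those files, where V.H applies, or through the IX.F route, where all events are kept.

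**Step 3: how many people.** The upper bound is 11 of 180 planned participants: 11/180 = 6.1%. The true number may be lower at each stage:

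- Enrolment can precede randomisation by up to four weeks (V.A). V.H itself leaves open that some of the 11 were not yet randomised: "with the exception that participants who were previously randomized will retain their original treatment group assignment".
- Varenicline is offered, not required, and the prescription may be delayed (V.A.4, V.B).
- Monitoring visits begin one week after the quit date, so side-effect records from those visits exist only for people who got that far.
- Not everyone need restart.

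The documents give none of these counts, so the range is 0 to 11.

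**Step 4: could an event plausibly be omitted?** The plan gives no event rates, so the rates here are assumptions. With m restarters who took varenicline before the pause, and a per-person chance p of a given event during the first course, the chance that at least one had it is 1 − (1 − p)^m.

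| p (assumed) | m = 3 | m = 6 | m = 11 |
|---|---|---|---|
| 1% | 3% | 6% | 10% |
| 5% | 14% | 26% | 43% |
| 10% | 27% | 47% | 69% |
| 30% | 66% | 88% | 98% |

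For example, with p = 5% and m = 11, 1 − 0.95^11 = 43%. Common side effects could well be missing from a results table; a rare event probably would not be at issue.

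**The case against.** The strongest reply is that the sentence belongs to a paragraph on REDCap forms and governs analyses, while adverse events travel separately and in full through IX.F and IX.H. On that reading nothing is lost to oversight, and VI.C names no safety analysis for events to fall out of. Much of this stands: the point is confined to what is analysed and reported. It does not remove the point. Varenicline use is an analysed outcome, and because VI.C is silent on safety, the V.H sentence is the only written instruction on which of these participants' monitoring data count when results are tabulated.

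A reader might infer more than the documents support:

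- **That pre-pause data are thrown away.** They are archived, repeatable forms gain new instances, and overwrites are logged.
- **That V.H contradicts the promise in IX.F to report all adverse events.** It does so only if analyses are taken to include regulatory safety reporting, which the text does not say.
- **That the rule is selective, keeping pre-pause data for non-restarters and dropping it for restarters.** The plan does not say how non-restarters are analysed.
- **That first-course intolerance could escape notice at restart because primary care permission is tied to the latest survey.** V.H messages all primary care providers again and applies V.A.4, under which the clinician also reviews the health record and self-reported history. V.B lets the clinician seek the provider's input on anything found there.
- **That omitted records would hide evidence on nitrosamine harm.** VII.B describes that concern as one of prolonged exposure, which short-term checklists from at most 11 people would not inform.

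**Conclusion.** The concern holds in limited form. A stated rule, followed as written, gives an incomplete tabulation of side effects, C-SSRS results and varenicline exposure for restarted participants. It affects between 0 and 11 people, at most 6.1% of the planned sample, and leaves every primary and secondary efficacy result unchanged. The conclusion rests on reading the sentence literally. The probabilities of omission rest on assumed event rates and assumed numbers exposed. The small scale makes this a correction worth making, not a threat to the trial; the near-zero cost is the reason to make it.

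**What to change.** In Section V.H, restrict the sentence to baseline, smoking-outcome and other efficacy data. Add that reported summaries of adverse events, side effects, C-SSRS results and varenicline exposure include all records from first enrolment, under the original arm, with pre-pause and post-restart periods shown separately. State there, or in VI.C, how many of the 11 were randomised, took varenicline and restarted, once known.

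This needs one or two sentences and some data management to bring the archived records into the safety dataset. It needs no new data collection and no change to the efficacy analysis.
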